### **9.3 Populations for Analysis**

The following populations are defined:

Population	Description
PK	subjects who have received at least 1 dose of AMG 340 and have at least 1 PK sample drawn post dose

ADA	subjects who have received at least 1 dose of AMG 340 and have at least 1 ADA sample drawn post dose
RECIST 1.1 Evaluable	subjects who have received at least 1 dose of AMG 340, have measurable disease per RECIST 1.1 at baseline and have the opportunity to be followed for at least 6 weeks from start of AMG 340 treatment.
PSA Response Evaluable	subjects who have received at least 1 dose of AMG 340, have a measurable (ie, $> 0$ ) PSA at baseline, and have the opportunity to be followed for at least 9 weeks from start of AMG 340 treatment.
DLT-evaluable	subjects who are evaluable for DLTs. A subject is considered “DLT Evaluable” if the subject has completed at least the first full treatment cycle or has experienced a DLT during the first treatment cycle
Safety	subjects who have received at least 1 dose of AMG 340

ADA = antidrug antibody; DLT = dose limiting toxicity; PK = pharmacokinetic; PSA = prostate specific antigen; RECIST = Response Evaluation Criteria in Solid Tumor

### **9.3.1 Covariates**

Not applicable for this study.

### **9.3.2 Subgroups**

## **9.4 Statistical Analyses**

The statistical analysis plan will be developed and finalized before database lock. Below is a summary of the timing and methods for the planned statistical analyses.

### **9.4.1 Planned Analyses**

#### **9.4.1.1 Interim Analysis and Early Stopping Guidelines**

Amgen will conduct evaluations of the treatment and outcome of the CRS events treated with siltuximab on an ongoing basis to assess if the threshold for pausing siltuximab treatment has been reached as outlined in the table below. If these stopping rules are met, an ad hoc DLRT will be triggered to review safety data and available PK, PD, and efficacy data. If recommended by DLRT, the use of siltuximab will resume. The stopping rules to trigger an ad hoc DLRT to review siltuximab treatment use a Bayesian approach proposed by Thall, et al (1995); an ad hoc DLRT will be triggered if the posterior probability that the CRS progression to grade 3 rate is greater than 30% is  $> 80\%$  or the posterior probability that the CRS progression to grade 4 rate is greater than 10% is  $> 80\%$ ; or observation of any grade 5 CRS after the event has been treated with

siltuximab. The stopping boundaries presented below assume a prior distribution of Beta (0.6, 1.4) for progression to grade 3 CRS and a prior distribution of Beta (0.2, 1.8) for progression to grade 4 CRS. The evaluations could occur more frequently if necessary to address emerging safety concerns. If the triggered ad hoc DLRT coincide with regular DLRT, they may be combined.

**Table 9-1. The Criteria for Evaluating the Use of Siltuximab**

Number of subjects treated with siltuximab	Trigger DLRM if severity of any CRS event treated with siltuximab progresses to Grade 5	
	Or the number of subjects with severity of CRS progressed to Grade 3 after being treated with siltuximab is	Or the number of subjects with severity of CRS progressed to Grade 4 after being treated with siltuximab is
5	≥ 3	≥ 2
10	≥ 5	≥ 3
15	≥ 7	≥ 3
20	≥ 8	≥ 4
25	≥ 10	≥ 5
30	≥ 12	≥ 5
35	≥ 13	≥ 6
40	≥ 15	≥ 6

CRS = cytokine release syndrome; DLRM = dose level review meeting

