Sites are required to have tocilizumab or siltuximab (if tocilizumab is not available) on site for potential treatment of CRS. For administration of dexamethasone or tocilizumab after occurrence of CRS, follow guidance in [Table 6-6](#). Tocilizumab should be administered according to local prescribing information. If tocilizumab is not available, siltuximab (an anti-IL-6 monoclonal antibody) may be used in the management of cytokine release syndrome, following the criteria outlined in [Table 6-6](#). The recommended dose of siltuximab is 11 mg/kg administered over 1 hour as an intravenous infusion, consistent with the prescribing information for the treatment of multicentric Castleman's disease (Sylvant Prescribing Information), and the CARTOX Working Group Guidelines for CRS management (Neelapu, 2018). Siltuximab may be repeated if needed, in the event that CRS recurs after a subsequent infusion of AMG 340. Siltuximab may not be repeated in an individual subject that develops anaphylaxis to siltuximab, or gastrointestinal perforation after siltuximab.

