#### **6.2.1.2 Dose Priming**

Based on the nonclinical pharmacology of AMG 340, a lower rate of CRS is anticipated than with other T-cell-engaging bispecifics; however, based on the mechanism of action of AMG 340, the most likely DLT to occur is still CRS  $\geq$  grade 3. Cytokine release syndrome will be managed per Principal Investigator discretion and institutional guidelines (a guide for management of CRS is provided in [Table 6-6](#) if institutional guidelines have not been established). Definitions for adverse events, serious adverse events, and DLTs are provided in Section [8.4.6.1.1](#), [8.4.6.1.2](#), and [6.2.1.4.1](#), respectively.

If a grade  $\geq$  3 CRS event occurs in Cohort N (where N represents a Cohort number) during the DLT period, or at the discretion of the DLRT, a dose equal to or less than the dose for Cohort N will be designated as the ‘Priming Dose’ and dose administration in subsequent cohorts (Cohorts N+1 and on) may be modified as follows:

- On Cycle 1 Day 1, subjects will receive the Priming Dose.
- On Cycle 1 Day 8, subjects will receive the full dose corresponding to the cohort in which they have been enrolled.

Note: a second priming dose may be introduced based on emerging data.

If a subject experiences CRS grade  $\geq$  2, or any other grade  $\geq$  2 toxicity after receiving a priming dose that is not unequivocally due to the subject’s underlying malignancy or other extraneous cause, administration of the full dose on cycle 1 day 8 must await approval by the Amgen Medical Monitor(s). At a minimum, CRS must have resolved to

grade  $\leq$  1 before the next is administered. The dose and timing of the full dose for such a subject may be modified at the discretion of the Amgen Medical Monitor and the Investigator; if the subject has their full dose reduced in cycle 1, the subject will be considered DLT-unevaluable and should be replaced. In subsequent cycles, subjects will receive the full dose on day 1.

Following implementation of a priming dose, if administration of the full dose is delayed in cycle 1, the DLT period for that subject should be extended to the same degree (eg, if the full dose is delayed by 4 days, the DLT period will also be extended 4 days). For clarity, treatment-emergent adverse events meeting criteria for a DLT will be treated as a DLT whether they occur after administration of the priming or the full dose.

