**Table 6-6. AMG 340 Dose Modification Guidelines for Adverse Events**

Grade	Description of Severity a	Interruption/Delay	Specific Management	Restart Guidance	Permanent Discontinuation
Cytokine Release Syndrome continued (see Section 6.2.1.6 for additional guidance and grading scale details)					
2	
Symptoms require and respond to moderate intervention
 
 
Feverb: <math>\geq 38^{\circ}\text{C}</math> WITH
 
Hypotension: not requiring vasopressors AND/ORc
 
Hypoxia: requiring low-flow nasal cannulad or blow-by
 
	
Delay AMG 340 until event improves to CRS grade <math>\leq 1</math>.
	
Administer:
 
 
Symptomatic treatment (eg, paracetamol/acetaminophen) for fever
 
Supplemental oxygen when oxygen saturation is <math>< 90\%</math> on room air (low-flow [<math>\leq 6</math> L/minute] nasal cannula or blow-by)
 
IVF when systolic blood pressure is <math>< 85</math> mmHg. Persistent tachycardia (eg, <math>> 120</math> bpm) may also indicate the need for intervention for hypotension.
 
 
Monitor:
 
 
CRS symptoms including temperature, blood pressure, and pulse oximetry
 
Fluid status, maintain IVF as needed
 
Cardiac and other organ function
 
Consider Chest X-Ray and obtaining appropriate cultures to rule out infection
 
 
For subjects with rapid onset (<math>< 4</math> hours from start of infusion), extensive co-morbidities or poor performance status, strong suggestion to manage per grade 3 CRS guidance below.
 
Thrombocytopenia occurring in the setting of CRS can be managed per Section 6.2.1.4 and/or per institutional guidelines.
	
 
The next infusion may be administered if all of the following criteria are met: 
 
If CRS occurred during AMG 340 infusion, infusion has been interrupted for at least 72 hours
 
Resume AMG 340 at same dose or reduce to next lower dose if clinically indicated.
 
The event has resolved to grade <math>\leq 1</math> prior to restarting treatment
 
 
 
	
If there is no improvement to CRS <math>\leq</math> grade 1 within 7 days

Abbreviations and footnotes defined on last page of table.

Page 5 of 19

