Cytokine Release Syndrome continued (see Section 6.2.1.6 for additional guidance and grading scale details)					
			
 
If tocilizumab is not available, siltuximab (an anti-IL-6 monoclonal antibody) may be used in the management of CRS. The recommended dose of siltuximab is 11 mg/kg administered over 1 hour as an intravenous infusion, consistent with the prescribing information for the treatment of multicentric Castleman's disease (SYLVANT® Prescribing Information, 2019), and the CARTOX Working Group Guidelines for CRS management (Neelapu, 2018). Siltuximab may be repeated if needed, in the event that CRS recurs after a subsequent infusion of AMG 340. Siltuximab may not be repeated in an individual subject that develops anaphylaxis to siltuximab, or gastrointestinal perforation after siltuximab.
 
 
Monitor:
 
 
CRS symptoms including temperature, blood pressure, and pulse oximetry
 
Fluid status, maintain IVF as needed
 
Consider Chest X-Ray and obtaining appropriate cultures to rule out infection
 
If refractory hypotension (after 2 fluid boluses), consider ECHO
 
 
Admit to intensive care unit for close clinical and vital sign monitoring per institutional guidelines.
 
Thrombocytopenia occurring in the setting of CRS can be managed per Section 6.2.1.4 and/or per institutional guidelines.
		

Page 7 of 19

Abbreviations and footnotes defined on last page of table.

Table 6-6. AMG 340 Dose Modification Guidelines for Adverse Events

Grade	Description of Severity a	Interruption/ Delay	Specific Management	Restart Guidance	Permanent Discontinuation
Cytokine Release Syndrome continued (see Section 6.2.1.6 for additional guidance and grading scale details)					

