			
 
If tocilizumab is not available, siltuximab (an anti-IL-6 monoclonal antibody) may be used in the management of CRS, following the criteria outlined in the Management of Adverse Events table. The recommended dose of siltuximab is 11 mg/kg administered over 1 hour as an intravenous infusion, consistent with the prescribing information for the treatment of multicentric Castleman's disease (SYLVANT® Prescribing Information, 2019), and the CARTOX Working Group Guidelines for CRS management (Neelapu, 2018). Siltuximab may be repeated if needed, in the event that CRS recurs after a subsequent infusion of AMG 340. Siltuximab may not be repeated in an individual subject that develops anaphylaxis to siltuximab, or gastrointestinal perforation after siltuximab.
 
 
Monitor:
 
 
CRS symptoms including temperature, blood pressure, and pulse oximetry
 
Fluid status, maintain IVF as needed
 
Consider Chest X-Ray and obtaining appropriate cultures to rule out infection
 
If refractory hypotension (after 2 fluid boluses), consider ECHO
 
 
Admit to intensive care unit for close clinical and vital sign monitoring per institutional guidelines.
 
Thrombocytopenia occurring in the setting of CRS can be managed per Section 6.2.1.4 and/or per institutional guidelines.
		

Abbreviations and footnotes defined on last page of table.

Page 9 of 19

Table 6-6. AMG 340 Dose Modification Guidelines for Adverse Events

Grade	Description of Severity a	Interruption/ Delay	Specific Management	Restart Guidance	Permanent Discontinuation
Tumor Lysis Syndrome (TLS) – Grading according to Cairo-Bishop Criteria (see Section 11.11)					

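### The grade 3 limb of the siltuximab pause rule keeps subjects who cannot have the event in its denominator, so its sensitivity depends on an unstated case mix

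*Protocol*

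**What the plan says.** Protocol Section 9.4.1.1 and SAP Section 7.1 have the sponsor review siltuximab-treated CRS "on an ongoing basis to assess if the threshold for pausing siltuximab treatment has been reached as outlined in the table below". For the grade 3 limb the criterion is that "the posterior probability that the CRS progression to grade 3 rate is greater than 30% is" above 80%, with a Beta(0.6, 1.4) prior. The grade 4 limb uses a 10% limit and a Beta(0.2, 1.8) prior, and any grade 5 CRS also triggers.

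Table 9-1 turns this into counts for 5, 10, ... 40 subjects treated with siltuximab. The grade 3 column is headed "Or the number of subjects with severity of CRS progressed to Grade 3 after being treated with siltuximab is" and gives 3, 5, 7, 8, 10, 12, 13 and 15. Nothing restricts the row count by CRS grade at treatment.

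On when siltuximab is given:
- Section 6.1.5: "siltuximab (an anti-IL-6 monoclonal antibody) may be used in the management of cytokine release syndrome, following the criteria outlined in" Table 6-6.
- Table 6-6, grade 3 row: "If tocilizumab is not available, siltuximab (an anti-IL-6 monoclonal antibody) may be used in the management of CRS". Grade 4 row: "may be used in the management of CRS, following the criteria outlined in the Management of Adverse Events table".
- The grade 1 and 2 rows do not name siltuximab. For rapid onset, extensive comorbidity or poor performance status they carry a "strong suggestion to manage per grade 3 CRS guidance below".
- Section 6.2.1.2: "Cytokine release syndrome will be managed per Principal Investigator discretion and institutional guidelines", with Table 6-6 as the guide where a site has no guideline of its own.

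**The concern.** The grade 3 limb asks whether siltuximab fails to stop milder CRS from becoming severe. Only a subject below grade 3 at treatment can answer that. A subject treated at grade 3 or 4 can become a grade 3 event in the same episode only by first being downgraded, which Section 6.2.1.6 allows, and then worsening again. Such subjects add to the row count and hardly ever to the event count, so the estimated rate is pulled below the progression rate among those at risk.

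Two further points are undefined: whether a move from grade 2 straight to grade 4 counts in the grade 3 column, and how to place a subject treated in more than one CRS episode, which Section 6.1.5 permits.

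At stake is a review trigger that can stay silent although every subject who could have progressed did so.

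**Working it through.** **Inputs.** Priors, limits and the 80% cut-off come from Section 9.4.1.1, and the boundaries from Table 9-1. The share s of treated subjects who are below grade 3 at treatment is not in the documents; I assume 0.4 to 1.0. The true progression rate q among those at risk is set at 60% (twice the limit) or 30% (at the limit). Subjects treated at grade 3 or above are assumed never to become grade 3 events.

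**Step 1: reproduce the table.** With x events in n subjects the posterior is Beta(0.6 + x, 1.4 + n − x), and the boundary b(n) is the smallest x with Pr(rate > 0.30) > 0.80. For n = 5, 10, ... 40 this gives 3, 5, 7, 8, 10, 12, 13, 15. The grade 4 column also reproduces, so all 16 printed values are right with n as all treated subjects.

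**Step 2: one example.** Ten are treated, 4 of them below grade 3, and all 4 progress. On 4 of 10 the posterior is Beta(4.6, 7.4) and Pr(rate > 0.30) = 0.71. The row needs 5, so it does not trigger. On 4 of 4 at risk it is Beta(4.6, 1.4) and 0.99. (The row for 5 treated would have fired earlier if at least three of the four events fell among the first five subjects.)

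**Step 3: when a row cannot fire.** A row needs b(n) events, so it cannot trigger if the realised at-risk share at that row is below b(n)/n: 3/5 = 60%, 5/10 = 50%, 8/20 = 40%, and at the lowest 13/35 = 37%.

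**Step 4: trigger chance.** After each treated subject, track m (number at risk) and x (events). A new subject leaves (m, x) unchanged with probability 1 − s, adds one at risk without an event with probability s(1 − q), and adds one at risk with an event with probability sq. Both rules look only after every fifth treated subject. The printed rule stops if x ≥ b(treated); the at-risk rule stops if x ≥ b(m). Only the denominator differs.

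Grade 3 limb, q = 60%:

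| s | 0.4 | 0.6 | 0.8 | 0.9 | 1.0 |
|---|---|---|---|---|---|
| 20 treated, as printed | 17% | 53% | 87% | 95% | 98% |
| 20 treated, at-risk denominator | 84% | 92% | 96% | 97% | 98% |
| 10 treated, as printed | 12% | 35% | 64% | 77% | 87% |
| 10 treated, at-risk denominator | 60% | 75% | 81% | 82% | 87% |

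Single-look check: with 20 treated and exactly 12 at risk, Pr(X ≥ 8) for Binomial(12, 0.6) is 0.438, against Pr(X ≥ 6) = 0.842 at the at-risk boundary.

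**Step 5: does ongoing review cure it?** Applying the posterior rule at every treated count, with 20 treated and q = 60%, gives 28 / 64 / 91 / 96 / 99% for the same s. More looks help a little; the dilution remains.

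**Step 6: false triggers.** With 20 treated and q = 30%, for s = 0.4 / 0.6 / 0.8 / 1.0: 2 / 6 / 17 / 33% as printed, and 27 / 30 / 31 / 33% with the at-risk denominator.

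**The case against.** **A rate per treated subject is a coherent quantity.** Neither document says that the 30% limit is conditional on starting below grade 3. Both limbs share one count and both priors carry weight 2 (0.6 + 1.4 and 0.2 + 1.8). On that reading nothing is miscalculated, and a reader who inferred an arithmetic error in the table would be wrong. What does not survive is the purpose: a limb that can stay silent when every at-risk subject progresses does not monitor progression.

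**Low s with many treated is unlikely.** This largely stands. With 20 treated, s = 0.4 means 12 subjects given siltuximab at grade 3 or above, and s = 0.6 means 8. Section 2.2.4.3 reports CRS in 9 of 23 dosed subjects and grade 3 CRS in 1 (4.3%, exact 95% CI 0.1% to 22%). Over about 100 subjects that rate gives about 4; the chance of 12 or more is 0.1% and of 8 or more 7%, before requiring that tocilizumab be unavailable each time. The interval is wide, so these cases are not excluded. Still, a reader might take 17% against 84% as the expected loss, and the documents do not support that. If use stays at grade 3 and 4, the number treated may never reach the first row of 5; if it reaches 20, use below grade 3 is probably common and s high.

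**A reader might also infer that the printed rule can never fire once fewer than 37% of treated subjects are expected to be at risk.** That holds only for the share realised at a row. With each subject at risk with probability 0.3 and all of those progressing, chance variation in the mix still gives a trigger 33% of the time by 20 treated.

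**Other protection exists.** Worsening from grade 3 falls to the grade 4 limb, with its stricter 10% limit, and to the grade 5 trigger. Reviews may be more frequent, and Section 9.4.2.3.2 plans a siltuximab subgroup analysis. This is true, but the grade 4 and 5 triggers act only after worse harm.

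**Conclusion.** The concern holds as a denominator fault in the grade 3 limb; the boundary arithmetic is sound. The realistic loss lies at small numbers treated, or at s near 0.8 and above. With 10 treated and a true 60% rate it is 17 points at s = 0.8 (64% to 81%) and 5 at s = 0.9 (77% to 82%); with 20 treated it is 9 and 2 points. It is nil if everyone is treated below grade 3, and large only if use follows the grade 3 and 4 rows closely while many subjects are treated.

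These sizes rest on the assumed s, on grade at treatment being independent between subjects, and on ignoring progression after a downgrade. The grade 4 limb has the same fault only for subjects treated at grade 4. The scope is one limb of a review trigger for a back-up drug, after which use may resume. It does not show that CRS goes unmonitored. The change is still worth making because the limb's sensitivity should not depend on case mix.

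**What to change.** Keep the priors, limits and 80% cut-off. In Protocol Section 9.4.1.1 with Table 9-1, and in SAP Section 7.1 with Table 7-1:

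1. Use as denominator only subjects whose CRS was below grade 3 (grade 3 limb) or below grade 4 (grade 4 limb) when siltuximab was started. Take each subject's first siltuximab-treated episode that qualifies.
2. Count progression to that grade or higher, so that a skipped grade is covered.
3. Tabulate boundaries by number at risk. For the grade 3 limb, 2 to 10 at risk: 2, 2, 3, 3, 3, 4, 4, 5, 5; 11 to 20: 5, 6, 6, 6, 7, 7, 7, 8, 8, 8. The printed values at multiples of five do not change.
4. Start the grade 4 limb at 3 at risk (2 of 3, 2 of 4), because the bare rule would fire on 1 of 1 (posterior 0.88) or 1 of 2 (0.81).
5. Look up these boundaries after every fifth treated subject. The example in the working then triggers: 4 events against a boundary of 3.

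Starting grade can be derived from the CRS event entries, which are made for each increase in grade (Section 6.2.1.6), and the concomitant therapy dates (Section 6.7.2), or it can be recorded in one CRF field.

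The cost is new column labels, extra boundary values, a short definition in each document, and more ad hoc reviews when s is below 1. At a true 30% rate and 20 treated, the false-trigger chance never exceeds the 33% that the printed table already has when all are at risk. Looking at every at-risk count instead would raise it to between 33% and 46%, which is why looks after every fifth treated subject are preferred.

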#### **9.4.1.2 Primary Analysis**

The primary analysis will occur 6 months following the enrollment of the last subject in Part B. The data will be analyzed once they have been entered, cleaned, and locked.

#### **9.4.1.3 Final Analysis**

The final analysis will occur after all subjects have ended the study. The data will be analyzed once they have been entered, cleaned, and locked.

### **9.4.2 Methods of Analyses**

#### **9.4.2.1 General Considerations**

Descriptive statistics will be provided for selected demographics, safety data by dose, dose schedule, and time as appropriate. Descriptive statistics on continuous data will include means, medians, standard deviations, and ranges, while categorical data will be summarized using frequency counts and percentages. Graphical summaries of the data may also be presented.

#### 9.4.2.2 Efficacy Analyses

Endpoint/ Estimand	Statistical Analysis Methods
Primary	Not applicable
Secondary	The proportion of subjects with an OR per RECIST 1.1 along with the corresponding exact 95% CI will be calculated using the Clopper-Pearson method (Clopper and Pearson, 1934); similarly, the proportion of subjects, 95% CI will be tabulated for PSA response. Kaplan-Meier quartiles, rates and curves will be used to summarize OS, rPFS, 6-month landmark rPFS, PSA PFS, time to progression (radiographic and PSA), time to symptomatic skeletal events (SSE), and DOR.

Listings may be provided instead of summary tables if the number of subjects for analysis is small.

#### 9.4.2.3 Safety Analyses

##### 9.4.2.3.1 Analyses of Primary Safety Endpoint(s)

Endpoint/Estimand	Statistical Analysis Methods
Primary	Unless otherwise specified, statistical analyses on safety endpoints will be done using subjects from the Safety Analysis Set, which includes subjects that are enrolled and received AMG 340. The analysis of DLTs will be conducted on the DLT Analysis Set. Subject incidence of DLT will be tabulated by planned dose level. The statistical analysis methods for other safety endpoints are described in Sections 9.4.2.3.2 through 9.4.2.3.6. Descriptive statistics for the continuous variables and the frequencies/percentages for the discrete variables will be provided.

